#### 9.2.18.3 Severe Adverse Events

Severe AEs are defined as events with a severity of Grade 3 or higher.

\* Instrumental activities of daily living refer to preparing meals, shopping for groceries or clothes, using the telephone, managing money, etc.

† Self-care activities of daily living refer to bathing, dressing and undressing, feeding self, using the toilet, taking medications, and not bedridden

## 9.2.18.4 Serious Unexpected Suspected Adverse Reaction

A serious AE deemed related to the study drug (adverse reaction) is considered "unexpected" if it is not listed in the Investigator's Brochure (i.e., ECG QT prolonged, Hypertension, Rash [rash, infusion site rash and rash erythematous]) or is not listed at the specificity or severity that has been observed.

#### 9.3 Analysis Windows

Clinical visits may occur outside protocol-specified windows. Therefore, instead of relying solely on visit labels in the clinical database, analysis visits and their windows are defined using Study Day (See Section 9.2.2). For the purposes of data analysis and summary, assessments and/or measurements will be flagged based on the collection date/time that is closest to the protocol-scheduled time point (or target Study Day). Analysis visit windows are presented in by type of assessments and/or measurements.

**Table 6** Visit Analysis Windows (Clinic visits only)

Protocol Specified Visit	Target Study Day	Start (days)	Stop (days)
Screening	-114	low	-1
Cycle 1 Day 1	1	1	4
Cycle 1 Day 8	8	5	11
Cycle 1 Day 15	15	12	18
Cycle 1 Day 22	22	19	25
Cycle 2 Day 1	29	26	32
Cycle 2 Day 8	36	33	39
Cycle 2 Day 15	43	40	46
Cycle 2 Day 22	50	47	53
Cycle 3 Day 1	57	54	60
Cycle 3 Day 8	64	61	67
Cycle 3 Day 15	71	68	74
Cycle 3 Day 22	78	75	81
Cycle 4 Day 1	85	82	88
Cycle 4 Day 8	92	89	95
Cycle 4 Day 15	99	96	102
Cycle 4 Day 22	106	103	109
Cycle 5 Day 1	113	110	116
Cycle 5 Day 8	120	117	123
Cycle 5 Day 15	127	124	130
Cycle 5 Day 22	134	131	137

Protocol Specified Visit	Target Study Day	Start (days)	Stop (days)
Cycle 6 Day 1	141	138	144
Cycle 6 Day 8	148	145	151
Cycle 6 Day 15	155	152	158
Cycle 6 Day 22	162	159	165
Cycle 7 Day 1	169	166	172
Cycle 7 Day 8	176	173	179
Cycle 7 Day 15	183	180	186
Cycle 7 Day 22	190	187	193
Cycle 8 Day 1	197	194	200
Cycle 8 Day 8	204	201	207
Cycle 8 Day 15	211	208	214
Cycle 8 Day 22	218	215	221
Cycle 9 Day 1	225	222	228
Cycle 9 Day 8	232	229	235
Cycle 9 Day 15	239	236	242
Cycle 9 Day 22	246	243	249
Cycle 10 Day 1	253	250	256
Cycle 10 Day 8	260	257	263
Cycle 10 Day 15	267	264	270
Cycle 10 Day 22	274	271	277
End of Treatment	Treatment End Date	Study Day <= (ADSL.TRTEDT - ADSL.TRTSDT + 1)	
Follow-up	Treatment End Date + 30 Days (± 7 days)	Study Day > (ADSL.TRTEDT - ADSL.TRTSDT + 1)	high

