6.9.3 End-of-Treatment Visit

The EOT should be completed within \pm 7 days of the last dose of tarloxotinib. The following will be assessed or measured at EOT:

- Complete physical examination
- Weight
- Vital signs
- ECG (12-lead)
- Hematology panel
- Serum chemistry panel
- Pregnancy test
- Urine (dipstick acceptable)
- Blood sample for biomarkers (e.g., ctDNA)
- Concomitant medications
- Assess AEs
- Record the date and reason for the decision to discontinue study treatment

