Approximately 248 subjects were planned for enrollment on the study to yield 215 evaluable subjects, 43 subjects per cohort. A total of 41 subjects were enrolled in cohorts A, B and C. No subjects were enrolled on cohorts C and D. All cohorts used a Simon's 2-stage design. In the first stage, 21 subjects were accrued. If more than 3 subjects in a cohort had a partial or complete response, up to 22 additional subjects could have been enrolled to the cohort, for up to a total of 43 subjects per cohort. However, if there were 3 or fewer responses among these 21 subjects, the cohort would be stopped based on futility.

Subjects received taroxontinib 150 mg/m^2 administered as a weekly 1-hour IV infusion on Days 1, 8, 15, and 22 of each 28-day cycle until disease progression or unacceptable toxicity (e.g., hepatotoxicity meeting Hy's law criteria or serious arrhythmias of ventricular origin).

\* Cohorts B1 and/or D were not pursued, at the discretion of the Sponsor

Subjects were expected to receive up to 10 cycles of treatment. The total study duration was estimated to be 36 months, including approximately 24 months for accrual and approximately 12 months for follow-up after the last subject was enrolled. Upon completion of the end of treatment visit, subjects returned to the clinic within 30 days following their last dose for a Follow-up visit. Clinical visits during the Treatment Period and Follow-up Period included efficacy, biomarkers, safety, and pharmacokinetic (PK) assessments. Figure 1 depicts study visits from Screening Period to Follow-up Period. The maximum duration of Study RAIN-701 per subject was expected to be up to 338 days (i.e., a maximum of 28-day Screening Period, a Treatment Period consisting of a maximum of ten 28-day treatment cycles, and a 30-day safety Follow-up Period). Assessments and procedures for evaluation of safety, efficacy, PK, and biomarkers were conducted per the protocol-specified schedule (see Table 2).

Figure 1 Schema of Study RAIN-701

Days 1, 8, 15, and 22 of every 28-day cycle

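### SAP Table 6 closes the End-of-Treatment window on the last dose day and leaves the cycle windows open after it, with no rule for which row wins

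*SAP*

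**What the plan says.** SAP Section 9.3 bases visit assignment on dates: "instead of relying solely on visit labels in the clinical database, analysis visits and their windows are defined using Study Day". Records are then "flagged based on the collection date/time that is closest to the protocol-scheduled time point (or target Study Day". Table 6 has three kinds of post-baseline row:

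- **Cycle visits.** There are 40 fixed windows of target day ± 3 (Cycle 1 Day 1 runs from Day 1 to Day 4), for example "Cycle 2 Day 1 29 26 32" (target, start, stop). None has a treatment-end condition.
- **End of Treatment.** The target is the treatment end date and the window is "Study Day <= (ADSL.TRTEDT - ADSL.TRTSDT + 1".
- **Follow-up.** The target is "Treatment End Date + 30 Days (± 7 days" and the window is "Study Day > (ADSL.TRTEDT - ADSL.TRTSDT + 1", with no upper limit.

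No order of precedence is given among these rows.

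On the visit itself, Protocol Section 6.9.3 allows EOT within 7 days either side of the last dose. Protocol Section 5.3 says the visit follows discontinuation of treatment. The first footnote to SAP Table 2 puts it on Day 28 of the cycle just finished, which is 6 days after a Day 22 dose. Protocol Section 6.9.4 puts the safety follow-up 30 ± 7 days after the last infusion.

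**The concern.** An analysis window should catch the visit it is named after. As written, the EOT row catches everything up to the last dose and nothing after it, so an EOT visit held after the last dose can only be Follow-up or a cycle visit. Because the cycle windows continue to Day 277 whatever the subject's last dose, records from subjects who have stopped can also satisfy the row of a visit at which they were not dosed.

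What is at stake is the by-visit safety tables (SAP Sections 14.2 to 14.4) in a report whose stated main purpose is a comprehensive safety analysis. The cohorts have 11, 22 and 8 subjects, so a few misassigned records can change a late-cycle row. Two programmers working from Table 6 could also produce different tables.

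**Working it through.** **Inputs.** Dosing on Days 1, 8, 15 and 22 of 28-day cycles (SAP 6.2.1); windows from SAP Table 6; EOT timing from Protocol 6.9.3; follow-up timing from Protocol 6.9.4. TRTEDT is not defined in the SAP. I read it as the last dose date because SAP 9.2.16.5 uses the same expression with the last and first dose dates, and because the +30-day Follow-up target then agrees with the protocol.

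**Reproducing Table 6.** Target = 28 × (cycle − 1) + 1, 8, 15 or 22; window = target ± 3, floored at Day 1. This returns all 40 cycle rows, from Cycle 1 Day 1 (1 to 4) to Cycle 10 Day 22 (target 274, window 271 to 277).

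**EOT visits 1 to 7 days after the last dose.** Each of the 40 dosing days is taken in turn as the last dose: 40 × 7 = 280 combinations.

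| Rule met | Combinations |
|---|---|
| EOT window | 0 of 280 |
| Follow-up window | 280 of 280 |
| Window of the last dosed visit (+1 to +3) | 40 × 3 = 120 |
| Window of the next, undosed visit (+4 to +7) | 39 × 4 = 156 |
| No cycle window (+4 to +7 after Cycle 10 Day 22) | 4 |

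The undosed-visit problem therefore starts at +4, not +1.

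**Follow-up visits at +23 to +37.** 40 × 15 = 600 combinations. All meet the Follow-up rule. Those beyond Day 277 number 2 × 3 + 7 × 4 + 6 × 5 = 64, so 600 − 64 = 536 also meet an undosed cycle window.

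**Does the closest-to-target rule repair it?** Take a last dose on Day 22. The targets are Day 22 (EOT), Day 29 (Cycle 2 Day 1), Day 50 (Cycle 2 Day 22) and Day 52 (Follow-up).

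- An EOT visit on Day 26 is 3 days from Cycle 2 Day 1, 4 from the EOT target and 26 from Follow-up. Days 26 to 29 are all closest to Cycle 2 Day 1.
- An EOT visit on Days 23 to 25 is as close to Cycle 1 Day 22 as to EOT, but is outside the EOT window. Within the Cycle 1 Day 22 row, the dosing-day record is closer.
- A follow-up visit on Day 52 is 0 days from Follow-up and 2 from Cycle 2 Day 22, so it goes to Follow-up. Within +23 to +37, only +30 to +32 are uniquely closest to Follow-up, and +29 ties.

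The rule therefore rescues some follow-up visits and no EOT visit held after the last dose.

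**What fills the EOT row.** With no lower bound, every on-treatment record qualifies, and the one closest to the treatment end date is a dosing-day record. If the true EOT record goes to Follow-up, the 30-day visit is closer to that target and displaces it.

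**By assessment.** Serum chemistry is scheduled at every dosing visit, so the counts above apply to it. Haematology is scheduled in-cycle only on Day 1. Counting only undosed Day 1 windows:

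- EOT: last dose on Day 22 of Cycles 1 to 9, 9 × 4 = 36 of 280.
- Follow-up: after a Day 1 last dose, 9 × 7 = 63; after Day 8, 9 × 2 = 18; after Day 15, none; after Day 22, 8 × 6 = 48. The total is 129 of 600.

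**The case against.** Several counter-arguments have force.

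- **Entry into cycle visits is not certain.** If a programmer gives the Follow-up condition priority, no post-treatment record reaches a cycle row. This stands: the documents support saying that such records could be mixed in, not that they will be. It does not help the EOT row, which still excludes the visit.
- **The counts are not rates.** They weight every last-dose day equally and leave out EOT visits on days −7 to 0, which the protocol allows and which do meet the EOT window. Including them adds 39 × 7 + 40 = 313 combinations (a Day 1 last dose has no earlier study day), and the undosed-visit share becomes 156 of 593, about 26%. A reader might infer that 56% (156/280) of EOT visits or 89% (536/600) of follow-up visits will be mislabelled. The documents give no distribution of visit days that would support this.
- **ECGs and vital signs are less exposed.** On treatment they are summarised at infusion-related time points, to which a single EOT or follow-up measurement does not naturally correspond. This stands.
- **Calling EOT values off-treatment says too much.** A continuing subject's pre-infusion Cycle 2 Day 1 sample is also taken about 7 days after a dose. True, but the row would still include subjects not dosed at that visit.
- **CRF visit labels may be used.** The SAP says it will not rely on them alone, which leaves room, but it states no rule by which a label overrides Table 6.
- **TRTEDT might mean something else.** SAP 9.2.3 ties completion of treatment to the EOT visit. If TRTEDT were that visit's date, the EOT row would catch the visit, but the Follow-up target would no longer match the protocol.

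A reader might also object that windows stop at Day 277 although treatment continues to progression. The SAP describes "a Treatment Period consisting of a maximum of ten 28-day treatment cycles" and Table 6 agrees with it. Nothing in the documents shows a subject dosed beyond Cycle 10, so this is not a defect on the text.

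**Conclusion.** The EOT row is wrong as written: under Table 6 an EOT visit held after the last dose cannot be analysed as EOT, and a dosing-day record can stand in its place. The overlap of cycle windows with EOT and Follow-up is a second defect. Its effect depends on a precedence the SAP does not state, and the closest-to-target rule settles it only in part. Both conclusions rest on reading TRTEDT as the last dose date.

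The reach is limited to by-visit descriptive summaries: mainly serum chemistry, less so haematology, vital signs and ECG. Treatment-emergent adverse events, worst-grade laboratory shifts, QTcF categories at any time, and the efficacy endpoints do not depend on these windows. This should be corrected before the tables are produced, but it does not threaten the report's main conclusions.

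**What to change.** Revise SAP Table 6 and add a few lines to Section 9.3:

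1. Define TRTEDT as the date of the last tarloxotinib dose.
2. Apply each cycle window only up to that date.
3. Assign EOT by the recorded EOT visit label or, where there is none, to days after the last dose through at least +7. An EOT visit on or before the last dose day needs the label to separate it from the cycle visit.
4. Start Follow-up after the EOT window, with target +30.
5. State that EOT and Follow-up take precedence over cycle windows.

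With these rules all 280 combinations at +1 to +7 become EOT, and all 600 at +23 to +37 become Follow-up only. Extend the cycle windows past Cycle 10 only if the locked database shows a subject dosed there. The cost is one table edit and a small programming change, with no new data.

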## 10 STATISTICAL AND ANALYSIS ISSUES

## **10.1** Adjustments for Covariates

No adjustments for covariates will be performed in the study.

## 10.2 Handling Dropouts or Missing Data

Missing data will not be imputed. Every effort will be made by the Sponsor to ensure completeness of data collection.

## 10.2.1 Handling of Laboratory Data

A retest value will be used if the first test is invalidated, e.g., specimen hemolyzed.

## 10.2.2 Handling of Safety Data

#### 10.2.2.1 Adverse Events

If the time of onset (before or after intake of study drug) cannot be determined whether an AE is treatment-emergent because of a partial onset date, the event will be counted as a TEAE.

Adverse events with incomplete start dates will be considered TEAEs, if:

- Day and month are missing and the year is equal to or after the year of the first date of study drug dosing;
- Month is missing and the year is after the year of the first date of study drug dosing;
- Day is missing and the year is equal to the year of the first date of study drug dosing and the month is equal to or after the month of the first date of study drug dosing; or
- Year is missing.

If severity or relationship of an AE to study drug is not recorded, the severity or relationship will be imputed as "severe" or relationship as "possibly related," for analysis purposes.

#### 10.2.2.2 Concomitant Medications

If start date of a medication is missing, the medication will be considered to have started prior to the study. Such a medication may also be considered concomitant, depending on the stop date or lack thereof. If the stop date of a concomitant medication is missing, then the medication will be treated as ongoing. If the start date of a medication is missing, the stop date will be used to determine whether or not it is concomitant. Medications with other incomplete start dates or end dates will be imputed as follows:

Incomplete medication start date/time:

- If only have a YEAR, impute as Jan. 1.
- Else if only have YEAR and MONTH, impute as Day 1 of month.
- Otherwise missing, no imputation.

Incomplete medication end date/time:

- If only have a YEAR, impute as December 31.
- Else if only have YEAR and MONTH, then impute to last day of the month.
- Otherwise missing, no imputation.

## 10.3 Multicenter Considerations

This trial will be conducted at 14 study centers in the United States, Canada, and other regions. Data from all study centers will be pooled for efficacy and safety analyses. Because the number of subjects at each center is likely to be small, no analyses will be performed by center. Subjects from all centers will be pooled for all analyses.

#### 10.4 Multiple Comparisons, Multiplicity

Efficacy variables will be assessed without adjustment for multiple comparisons.

#### 10.5 Active-Control Studies

There is no comparator in this study as all subjects are treated with tarloxotinib.

## 10.6 Examination of Subgroups

Efficacy variables will be assessed without examination of subgroups.

#### 11 STUDY SUBJECTS

#### 11.1 Subject Enrollment and Disposition

#### 11.1.1 Enrolled Subjects

An accounting of the study subjects will be tabulated. Subjects not completing the study will be listed along with the reason for their premature discontinuation. Reasons for premature discontinuation will be summarized.

Enrolled (Section 9.2.1) subjects will be summarized by cohort and overall.

#### **Treatment Periods**

- Number of subjects enrolled (ITT)
  - o Number (%) of subjects who discontinued from the study treatment
    - The primary reason for withdrawal from the study treatment
  - o Number (%) of subjects who completed the study
  - O Number (%) of subjects who discontinued from the study
    - ➤ The primary reason for withdrawal from the study

The percentages will be based on the total subjects who are enrolled (ITT).

A listing of disposition will be provided for all enrolled subjects.

#### 11.2 Protocol Deviations

Protocol deviations will be neither listed nor summarized because RAIN-701 was discontinued and this SAP will support an abbreviated clinical study report, which does not include protocol deviations per FDA guidance (Food and Drug Administration, 1999).

## 11.3 Demographics and Baseline Characteristics

Demographics and baseline characteristics will be summarized and listed for all treated subjects (ITT). Demographic characteristics will include age, sex, race, and ethnicity. A subject listing of demographics will be provided.

## 11.3.1 Key Baseline Demographics

The following parameters from each of the individual baseline and historical summaries will be summarized in a single summary:

- Age
- Age group, n (%)
- Sex, n (%)
- Race, n (%)
- Ethnicity, n (%)
- Smoking status, n (%)
- Baseline weight (kg)
- ECOG performance status, n(%)
- Mutation status, n (%)
- Stage at time of disease, n (%)
- Stage at time of study entry, n (%)

#### 11.4 Medical History

Medical history and current medical conditions will be mapped to preferred terms and system organ classes using the MedDRA® Dictionary (version 23.0) Medical history will be summarized by system organ class (SOC) and preferred term (PT) by cohort and overall for ITT subjects. A subject listing of general medical history will include start date/end date, verbatim medical history term, SOC, PT, and ongoing status (Yes, No). Additional subject listings of prior radiation therapy and prior surgeries will contain the start date and end date (if available) and

type of procedure. The subject listing of prior systemic therapies will include at a start date, end date, medication, reason the therapy ended, and best overall response.

#### 12 STUDY DRUG AND OTHER MEDICATIONS

#### 12.1 Exposure to Study Drug and Study Treatment Compliance

Summaries of study drug exposure and compliance will be summarized overall and by cohort. The source for study drug dosing and compliance is drug exposure.

The summaries will include total number of cycles initiated, the median (range) of cycles administered, and dose intensity (see definitions in Section 9.2.11) by cohort and overall. The denominators for percentages will be the number of subjects who received the study treatment.

#### 12.2 Prior and Concomitant Medications

Prior and concomitant medications (see definition in Section 9.2.10), will be summarized using WHO DD ATC class and preferred name. The summary results will be presented by cohort. Prior medications will be summarized by cohort. Concomitant medications will be summarized by cohort and overall.

These summaries will present the number and percentage of subjects using each medication. Subjects may have more than one medication within an ATC class and preferred name. At each summary level subjects are counted once if they reported one or more medications at that level. Each summary will be ordered by descending frequency of incidence of ATC class and preferred name within each ATC class.

All medications will be provided in a subject listing with flags indicating study drug dose level. The variables include, but not limited to: Start date/end date/ongoing, medication name, ATC class and preferred name, indication, dose, unit, form, frequency, and route.

#### 13 EFFICACY ANALYSES

## 13.1 Primary Analysis

The primary analysis was planned after all subjects stop tarloxotinib treatment until documented disease progression or unacceptable toxicity. The primary analysis will not be performed because RAIN-701 was discontinued and this SAP supports an abbreviated clinical study report. Additionally, efficacy analyses are unlikely to be significant because the sample size is small and the analyses will be underpowered. In place of formal primary analyses, selected efficacy endpoints will be summarized descriptively.

## 13.2 Primary Efficacy

The primary objective of this study is to evaluate the ORR of tarloxotinib as defined as a CR or PR according to RECIST v1.1 recorded from baseline until disease progression or death due to any cause.

The numbers and percentages of subjects meeting each response will be summarized, and the ORR will be summarized by cohort along with the corresponding 2-sided 95% CI calculated using the binomial exact method. All treatment responses and all tumor assessments will be listed.

The maximum percent reduction from baseline in the sum of target lesions will be displayed as a waterfall plot. The waterfall plot will have a y-axis that will be the maximum percent change from baseline in the sum of target lesions, and the x-axis will be each cohort and overall.

The best overall response (Section 13.3) will be reported similarly.

#### 13.3 Secondary Efficacy

The secondary efficacy objective is to evaluate further measures of antitumor activity of tarloxotinib including:

- Best overall response (Reporting as described in Section 13.2),
- Duration of response (Section 13.3.1),
- Disease control rate (Section 13.2),

- Progression-free survival (Section 13.3.2), and
- Overall survival (Section 13.3.2)

The additional secondary objectives of exploratory biomarkers of hypoxia in tumor tissue and plasma exposure to tarloxotinib and effects on cardiac repolarization will not have analyses or descriptive summarization of these endpoints due to the limited data basis.

#### 13.3.1 Duration of Response

DOR will be summarized using descriptive statistics (Section 9.1) for each cohort and overall. The DOR data will be listed for each subject.

#### 13.3.2 Survival Reporting

The PFS and OS will be summarized using the Kaplan-Meier method and displayed graphically by cohort and overall: Median event times and the corresponding 2-sided 95% CI will be provided. The number and % of subjects with disease progression or death will be provided. The number and % of subjects censored as well as reasons for censoring will be provided. A listing of survival data will be provided.

#### 13.4 Exploratory Objectives

The exploratory objectives are:

- To evaluate the concordance of EGFR mutation, HER2 mutation, and NRG1, EGFR,
   HER2, and HER4 fusion detection between tissue and plasma using ctDNA
- To evaluate exploratory biomarkers of hypoxia in tumor tissue including 6
   transmembrane epithelial antigen of the STEAP4 expression and ERBB family and cancer cell signaling pharmacodynamic markers
- To evaluate the pharmacokinetics of tarloxotinib and tarloxotinib-E in tumor tissue

Analysis and descriptive summary of these exploratory endpoints are outside the scope of this SAP.

